12-21% and 12-25%, respectively, have been reported. Dyspnea quantified by the Medical Research Council (MRC) scale improved by up to 2 steps (5) and 6-minutes walking distance improved by 51 meters (6). However, a new technique, robot-assisted diaphragmatic plication, is spreading and increasingly replacing VATS. (7). One small retrospective study of 43 patients found comparable results between these techniques with a 7% increase in FEV₁ in both groups. In this study, symptom improvement was not analysed. Other published studies on robot-assisted thoracic surgery are also single-center studies on small cohorts consisting of 11-46 patients (8-12), often focusing on surgical safety and complications. Lung function and radiological changes have also sometimes been measured along with retrospective evaluation of symptoms before and after the operation, a design with major methodological weakness. However, no significant complications have been reported, and patients seem to improve their lung function and their symptom burden (8-12). Prospective studies evaluating RATS diaphragmatic plication are lacking.

This prospective cohort study, the **R**obot-**a**ssisted **p**lication **in d**iaphragmatic para**ly**sis study (The RAPIDLY-study) aims to evaluate the short- and long-term effect of robot-assisted diaphragmatic plication on physical performance, subjective breathlessness, lung function, blood gases, and radiology at five Swedish university hospitals, Gothenburg, Linköping, Lund, Umeå, and Uppsala.

Method

Study design and population

This multicenter observational cohort study will include patients with symptomatic unilateral diaphragmatic paralysis persisting for ≥1 year (6), scheduled for RATS at thoracic surgery clinics in five Swedish university hospitals (Gothenburg, Linköping, Lund, Umeå, and Uppsala). The expected number of patients per center is estimated to 3-5 annually.

Exclusion criteria are inability to complete forms in Swedish, neuromuscular disease as the cause of diaphragmatic paralysis, and other significant causes of dyspnea and impaired physical capacity than diaphragmatic paralysis.

Patients will be assessed preoperatively and postoperatively after one to three months and after one and three years.

Assessments

Patient characteristics

Age, sex, height, and weight will be recorded. Body mass index (BMI) is calculated by dividing a person's weight by their height in meters squared.

Actiology of diaphragmatic paralysis, relevant co-morbidities and use of long-term oxygen therapy and/or mechanical ventilation will be recorded.

The date for symptom debut, if known, is recorded.

Smoking history is defined as current smoker, ex-smoker (smoking history of \geq 100 cigarettes and having quit smoking \geq 6 months ago), and never smoker (smoking history of <100 cigarettes) (13). Smoking is quantified by pack-years (the number of packs of

cigarettes a person has smoked daily, multiplied by the number of years they have smoked) (14).

Primary outcome

The patients' exercise capacity will be evaluated using the 6-minute walking distance (6MWD). The patients are asked to walk as far as possible on a flat, straight surface for six minutes, and the total distance walked is measured (15-17).

Secondary outcomes

Questionnaires

The **modified Borg Scale** is a tool with a range from 0 to 10 used to measure an individual's perceived level of breathlessness or muscle fatigue during physical activity, where 0 represents no breathlessness, and 10 represents maximal breathlessness (15). The **modified Medical Research Council** (mMRC) dyspnea scale is used to assess the severity of breathlessness. The scale ranges from 0 to 4, with higher scores indicating more significant breathlessness (18).

The **Dyspnea-12** is a questionnaire used to measure the severity and quality of breathlessness in individuals with respiratory or cardiovascular conditions. It assesses dyspnea's physical and emotional aspects, providing a comprehensive picture of how breathlessness affects a person's life. It consists of 12 items, each with a scale range between 0 (no dyspnea) and 3 (severe dyspnea) (19-21).

The **EQ-5D** is one of the most widely used tools for assessing health-related quality of life. It includes five dimensions: mobility, self-care, usual activities, pain/discomfort, and anxiety/depression. These dimensions create a descriptive profile that can be converted into a single summary index, where a score of 1.0 indicates perfect health. Additionally, the tool includes a Visual Analog Scale (VAS), ranging from 0 (worst imaginable health) to 100 (best imaginable health), for self-assessment of overall health status (22).

Spirometry

Spirometry will be conducted 15 minutes after bronchodilation (inhalation of 200 µg salbutamol) in both supine and upright positions. Body plethysmography and singlebreath DLCO measurement will be performed. Predicted values will be determined using reference equations from the Global Lung Function Initiative (GLI) (23).

One-minute sit-to-stand test (1-MSTST)

This test assesses a person's functional exercise capacity by recording the number of full sit-to-stand repetitions completed in 60 seconds (24).

The **Maximal Inspiratory Pressure (MIP)** test is a respiratory test that measures the strength of the inspiratory muscles, particularly the diaphragm. By inhaling as forcefully as possible in a handheld device, the maximum negative pressure generated is recorded (25).

Blood gas analysis

A capillary or arterial blood gas analysis obtains the partial pressure of Oxýgen and Carbon dioxide (PaCO2) and Base excess (BE). Pulse oximetry obtains oxygen saturation.

Chest X-ray

Chest X-rays are acquired in full inspiration and expiration in frontal and lateral views. The distance from the most cranial part of the lung to the highest part of the diaphragm in both frontal and side views are measured separately.

Computerised tomography (CT) of Thorax

A CT with a standard protocol to identify and quantify lower lobe atelectasis.

Adverse events

Operating time, chest-drain duration, length of hospitalisation, per- and postoperative complications such as pain, bleeding and infections, 30-day readmission and 30-days mortality are recorded.

Statistics

Descriptive statistics summarise the data, and inferential statistics compare group differences.

Associations with the outcomes will be analysed using multivariable regression models, including linear regression (for continuous outcome variables) and logistic regression (for categorical outcomes). Repeated measurements within individuals will be managed through multilevel, random-effects models.

Power calculation: Based on a standard deviation of 90 meters in the 6-minute walk test (6MWT) among the general population (16), and considering that the minimal clinically important difference (MCID) is 53 meters (17), a total of 45 patients is required.

	Baseline	1-3 months	12 months	3 years
		post-	post-	post-
		operatively	operatively	operatively?
Demographics	Х			
Height	Х			
Weight	Х	Х	Х	Х
BMI	Х	Х	Х	Х
Waist-hip ratio	Х	X	Х	Х
Co-morbidities	Х			
Smoking/PY	Х			
Indication for op	Х			
Questionnaires	Х	Х	Х	Х
(The modified				
Borg-scale,				
mMRC, Dyspnea-				
12, EQ-D5)				
6MWT	Х	Х	Х	Х

Table of study assessments

Body	Х	Х	X	X
plethysmography,				
dynamic				
spirometry in				
seated and				
supine position,				
and DLCO				
MIP	Х	Х	Х	Х
1 minute Sit-to-	Х	X	Х	Х
stand test				
Chest X-ray	Х	Х	Х	Х
CT-scan	Х	Х		
Saturation	Х	Х	Х	Х
Arterial/capillary	Х	X	Х	Х
blood gas				
Questionnaire		X	Х	Х
pain/adverse				
effects				

Ethical considerations

Robot-assisted diaphragm plication is performed at several university hospitals in Sweden and abroad. The patients in this study have been clinically approved for this surgery. They are not exposed to any additional risks in this study beyond being examined more thoroughly with surveys and questionnaires, lung function and performance tests, and chest X-rays before and after the surgical procedure. An application will be submitted to the Ethics Review Authority.

Relevance of research

Robot-assisted plication in diaphragmatic paralysis is a new operative method performed at many thoracic centres worldwide without being scientifically evaluated in prospective studies. This national multicenter study, with a large cohort by international standards and with validated, highly relevant outcome variables, is expected to gain significant attention among thoracic surgeons and pulmonary physicians worldwide. The study has been approved by the Swedish Ethical Review Authority, Dnr 2025-01028-01and, and is registered on ClinicalTrials.gov, Dnr 2025-01028-01.

Preliminary results

None.

References

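### The pain questionnaire has no preoperative administration, so pain reported on it after surgery cannot be cleanly split into new, worsened and pre-existing pain

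*Protocol*

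**What the plan says.** The study is a single-cohort observational study without a comparison group (Protocol, Study design and population). On visits it states: "Patients will be assessed preoperatively and postoperatively after one to three months and after one and three years".

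Pain appears in three places:

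- **Adverse events.** "per- and postoperative complications such as pain, bleeding and infections, 30-day readmission and 30-days mortality are recorded". Pain is the first example given. The section has no rule on onset, severity or attribution.
- **Table of study assessments.** The row for the pain/adverse effects questionnaire is empty at Baseline and marked at 1-3 months, 12 months and 3 years.
- **Secondary outcomes, Questionnaires.** Of the EQ-5D the protocol says "It includes five dimensions: mobility, self-care, usual activities, pain/discomfort, and anxiety/depression". The table lists this instrument in the Questionnaires row, marked at Baseline and at all three follow-ups.

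Under Patient characteristics, the aetiology of the paralysis is collected, and "relevant co-morbidities and use of long-term oxygen therapy and/or mechanical ventilation will be recorded". Pain is not named there.

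**The concern.** Bleeding and infection are events with an onset after the operation. Pain is a state, and it can be present beforehand. Patients enter after at least one year of symptomatic paralysis, and chest, shoulder or back pain could predate plication, for instance from whatever injury or earlier surgery caused the paralysis.

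If the dedicated instrument is first given after surgery, a patient who reports pain at 12 months may have had the same pain before, may have had milder pain, or may have had none. The questionnaire alone cannot distinguish these. With no control group there is no other reference for how much pain to expect without the operation. What is at stake is how postoperative pain can be interpreted, particularly at 12 months and 3 years, when pain still present is most likely to be read as a lasting effect of the procedure.

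This has to be settled in the protocol, because the assessment table decides what is collected and when. A later analysis plan cannot recover a preoperative answer that was never taken.

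**Working it through.** **1. Is the empty cell real?** In the extracted table the row keeps an empty first cell followed by three marks. The CT row likewise keeps its empty later cells. The blank therefore does not look like an extraction fault.

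**2. Is the row an exception?** The other rows measured more than once are weight, BMI, waist-hip ratio, the four questionnaires (one row), 6MWT, plethysmography/spirometry/DLCO, MIP, sit-to-stand, chest X-ray, CT, saturation and blood gas. That makes 12, and all 12 are marked at Baseline.

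**3. What preoperative pain information is there?**

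| Source | Before surgery | After surgery | What it can show |
|---|---|---|---|
| Pain/adverse effects questionnaire | no | 1-3 months, 12 months, 3 years | pain at follow-up, with no change score |
| EQ-5D pain/discomfort | yes | 1-3 months, 12 months, 3 years | within-patient change in general pain or discomfort; no site, no cause |
| Aetiology and co-morbidities | yes | no | possibly a reason for earlier pain, but not its presence or severity |

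A coarse comparison is thus available at every visit, but none on the dedicated instrument.

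**4. Size.** The protocol states no pain rate, so there is no figure to reproduce. The following is an illustration with assumed inputs. Let b be the share of patients with earlier pain that persists and is reported on the questionnaire, and q the risk of new pain in the others. The share reporting any pain after surgery is

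b + (1 − b) × q

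| b (assumed) | q = 10% (assumed) | q = 20% (assumed) |
|---|---|---|
| 0% | 10% | 20% |
| 10% | 0.10 + 0.90 × 0.10 = 19% | 0.10 + 0.90 × 0.20 = 28% |
| 20% | 0.20 + 0.80 × 0.10 = 28% | 0.20 + 0.80 × 0.20 = 36% |
| 30% | 0.30 + 0.70 × 0.10 = 37% | 0.30 + 0.70 × 0.20 = 44% |

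For scale, take the planned number: "a total of 45 patients is required". With q = 10% and b = 10%, 45 × 0.19 = 8.6 patients report pain, of whom 45 × 0.90 × 0.10 = 4.1 have new pain. With b = 30%, 45 × 0.37 = 16.7 report pain and 45 × 0.70 × 0.10 = 3.2 have new pain. The gap is 45 × b, that is 4.5 to 13.5 patients.

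The table also shows the ambiguity directly: 28% reporting pain fits b = 20% with q = 10% and equally b = 10% with q = 20%. A preoperative administration would tell these apart.

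**5. Reach.** The figure of 45 is derived for the 6-minute walk. Pain enters neither that calculation nor the primary outcome.

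**The case against.** The best defence starts from the row itself. It combines pain with adverse effects, and adverse effects of an operation cannot exist beforehand, so an empty Baseline cell is a natural entry. The items are not shown. They may ask about pain at the surgical site or pain since the operation, which have no preoperative answer. Item wording and attribution rules commonly sit in a case report form or analysis plan. Pain is also outside the stated aims, and no hypothesis rests on it.

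Much of this stands. The adverse-effects items need no baseline, the lack of an attribution rule in the protocol is not a fault in itself, and the matter is secondary. It does not remove the gap. If the items ask about pain in general, the comparator is missing. If they ask about pain since the operation, the split between new and old pain rests on the patient's recall, up to three years later. The protocol's own introduction criticises earlier robotic series for assessing symptoms retrospectively.

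Two stronger readings are tempting, and the document supports neither.

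- A reader might infer that pain present before surgery will be counted as a postoperative complication. No passage says so. The protocol does not state how a questionnaire answer becomes a complication, and on ordinary usage a postoperative complication arises from or after the operation.
- A reader might infer that the study can report only the prevalence of pain after surgery and cannot see relief. The EQ-5D item at baseline and at every follow-up contradicts this: it shows worsening and relief, though only of general pain or discomfort.

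**Conclusion.** The point holds as a limited design weakness. The dedicated pain instrument lacks a preoperative administration in a cohort without controls, so pain reported on it cannot be cleanly divided into new, worsened and pre-existing. EQ-5D softens the problem without solving it.

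The size is unknown. The 19-37% range against a true new-pain risk of 10% depends wholly on three assumptions: 10-30% of patients have earlier pain, it persists, and it is reported on the questionnaire. It describes uncorrected reports of any pain and is neither an estimate for this cohort nor a predicted complication rate. At b = 0 there is no discrepancy. The change is worth making because it is cheap and cannot be made retrospectively.

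**What to change.** - In the Table of study assessments, split the row and mark Baseline for the pain items, with the same items and the same definition of site as at follow-up. Leave the adverse-effects items postoperative only.
- State that postoperative pain on this questionnaire is reported as new or worsened from baseline at 1-3 months, 12 months and 3 years.
- Report change in EQ-5D pain/discomfort alongside, including for patients operated on before the change, for whom it will be the only before/after pain measure.

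**Cost.** One short form at a preoperative visit that already includes four questionnaires, and missing baseline pain for anyone already operated on. At 3-5 patients a year in each of five centres, accrual is 15-25 a year, so 45 patients take 45/25 = 1.8 to 45/15 = 3 years. The protocol reports no preliminary results. A change made early in accrual would still cover most of the cohort.

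### Does the planned logistic regression force the five-level mMRC score into two classes and put rare complications into a multivariable model?

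*Protocol*

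**What the plan says.** The relevant text is short and general.

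- **Statistics, models.** Associations with the outcomes are to be analysed by multivariable regression. The models are introduced by the word *including*, and two are then named: linear regression for continuous outcomes and "logistic regression (for categorical outcomes". No kind of logistic regression (binary, ordinal, multinomial) is specified.
- **Statistics, repeated data.** "Repeated measurements within individuals will be managed through multilevel, random-effects models".
- **Statistics, description.** Data are also to be summarised descriptively.
- **Secondary outcomes, Questionnaires.** On the mMRC: "The scale ranges from 0 to 4, with higher scores indicating more significant breathlessness". No cut-off and no two-class version is given.
- **Adverse events.** Complications are listed, and "30-day readmission and 30-days mortality are recorded". No model is named for any of them.
- **Introduction.** Of earlier robot-assisted series of 11 to 46 patients: "no significant complications have been reported". No rate is given.
- **Sample size.** "a total of 45 patients is required", justified on the 6-minute walk alone.

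**The concern.** Read quickly, the Statistics section looks like a two-way rule: continuous outcomes get linear regression, everything else gets logistic regression. The mMRC is neither continuous nor binary. If logistic regression is taken to mean binary logistic regression, the score needs a cut-off. A one-step gain that does not cross it then counts for nothing, and a cut-off chosen late could be chosen by result. Breathlessness is a stated aim of the study, and the introduction reports earlier benefit in steps of the MRC scale.

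The same reading sends complications, readmission and mortality into a multivariable model. With 45 patients and few events, such a model often cannot be estimated. At stake would be the power for one secondary outcome and the reliability of any odds ratios for safety events.

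**Working it through.** **1. The number 45.** Inputs from the Statistics section: "standard deviation of 90 meters in the 6-minute walk test (6MWT) among the general population" and "the minimal clinically important difference (MCID) is 53 meters". Assuming two-sided 5% and 80% power, which the protocol does not state: 2 × (1.960 + 0.842)² × 90² / 53² = 2 × 7.85 × 8100 / 2809 = 45.3. So 45 is reproduced to rounding. This is the size per group for two independent groups, or for paired data with zero correlation. Whether it suits a single cohort is a separate question, and nothing below depends on it.

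**2. Is a two-class split planned?** For the concern to hold, the list of models would have to be closed, the mMRC would have to count as categorical, and logistic would have to mean binary. The protocol states none of these. A cumulative-logit model with a patient random intercept, the natural ordinal choice, is a logistic model and a multilevel model. It already fits within the two modelling sentences.

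**3. Where does half the power come from?** It comes from an illustrative simulation whose inputs are assumed, not taken from the protocol: 45 pairs, latent normal score, patient SD 0.8, residual SD 0.6, cuts at -1.5, -0.5, 0.5 and 1.5, baseline mean 0.3 or 0.8. The total SD is √(0.64 + 0.36) = 1, the within-patient correlation is 0.64, and the cuts are 1.0 apart. A latent shift of 0.4 is therefore a mean change of at most about 0.4 mMRC step. A signed-rank test on all five levels is compared with a mid-p McNemar test after splitting at ≥2 or ≥3.

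| Latent shift | Mean change in steps | Five levels | Split |
|---|---|---|---|
| 0.4 | about 0.4 | 0.76 to 0.80 | 0.26 to 0.47 |
| 0.8 | about 0.75 | 1.00 | 0.87 to 0.98 |
| 1.0 | about 0.95 | 1.00 | 0.98 to 1.00 |

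The ranges cover both baseline means and both cuts; repeated runs differ by a few hundredths. The introduction cites improvement of up to 2 MRC steps. That is an upper bound, but it shows that a mean shift of 0.4 step is the pessimistic end.

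**4. Associations, which is what the logistic sentence covers.** Against a proportional-odds analysis, the efficiency of a split with proportion q above the cut is q(1 − q) / [(1 − Σp³)/3], where the p are the five class proportions. With the simulation's baseline mean of 0.3, p = 0.036, 0.176, 0.367, 0.306, 0.115. Then Σp³ = 0.085 and (1 − 0.085)/3 = 0.305.

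- Cut at ≥3: q = 0.421, efficiency 0.244/0.305 = 0.80. Where the ordinal analysis has 80% power, the split has Φ(2.802 × √0.80 − 1.960) = 71%.
- Cut at ≥2: q = 0.788, efficiency 0.167/0.305 = 0.55, power 55%.

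Over several assumed distributions, cuts near the median have efficiency 0.75 to 0.81 and power 68% to 71%. Off-centre cuts give 51% to 59%, and extreme cuts 10% to 43%. A sensible split therefore does not discard most of the information.

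**5. Complications.** No rate is given, so 5% to 20% is assumed.

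| Incidence | Expected events in 45 | Three-covariate logistic model without events or not estimable |
|---|---|---|
| 5% | 45 × 0.05 = 2.25 | about 57% of runs |
| 10% | 45 × 0.10 = 4.5 | about 20% |
| 20% | 45 × 0.20 = 9 | about 3% |

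These failures are real, but they belong to a model that the protocol does not assign to these events. Counts and percentages are already covered by the descriptive summary. Zero events in 45 would have an exact two-sided 95% upper limit of 1 − 0.025^(1/45) = 7.9%.

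**The case for a change.** The best case for the concern is that the sentence is the protocol's only stated modelling rule. It names no ordinal method, and many readers take logistic regression to mean the binary form. Complications, readmission and death are the most plainly categorical items in the protocol, so the rule seems to reach them. For small shifts the power loss is large: at 0.3 to 0.4 SD a cut at ≥2 kept 42% to 52% of the ordinal power, and a cut at ≥3 kept 55% to 62%.

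Three things stand. The sentence is coarse. A badly placed split would cost much power if the true change were small. A multivariable logistic model on two to five events would be unreliable if anyone fitted it.

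What does not stand is the step from a general sentence to a specific bad analysis. Naming an ordinal model for the mMRC and reporting rare events descriptively would make the plan more specific without contradicting it. Nor does the protocol predict few events: it reports what earlier series found about significant complications, while its own list also includes pain and infections.

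**Conclusion.** The concern does not hold. The two-class mMRC and the multivariable complication model are both inferred, and the protocol's wording allows the better alternatives. Choosing the type of logistic model, and how rare events are reported, is detail that a protocol commonly leaves to the SAP, which was not available here.

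The claimed halving of power is not a property of the plan. It needs a mean benefit of about 0.3 to 0.4 mMRC step or a poorly placed cut. At about 0.75 step the split has power 0.87 to 0.98 against 1.00, and near one step almost nothing is lost. These figures rest on an assumed latent-normal model with 45 complete pairs; the protocol gives no mMRC distribution and no complication rate.

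The consequence would be limited in any case. The primary outcome is the 6-minute walking distance, and breathlessness is also measured by the modified Borg scale (0 to 10) and the 12-item Dyspnea-12, which the argument about splitting the mMRC does not touch.

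### Does basing 45 patients on a 90 m general-population SD, with no SD of within-patient change, leave the study wrongly sized?

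*Protocol*

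**What the plan says.** The power paragraph in the Statistics section is one sentence. It begins "Based on a standard deviation of 90 meters in the 6-minute walk test (6MWT) among the general population (16" and ends "the minimal clinically important difference (MCID) is 53 meters (17), a total of 45 patients is required". Reference 16 is, by its title, a set of reference values in healthy people. The paragraph states no alpha, power, test, allowance for loss, SD of change or before-after correlation.

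The rest of the protocol describes a before-after study. The study "aims to evaluate the short- and long-term effect of robot-assisted diaphragmatic plication on physical performance". Under Study design and population, "This multicenter observational cohort study will include patients with symptomatic unilateral diaphragmatic paralysis", all of them scheduled for the same operation, and "Patients will be assessed preoperatively and postoperatively after one to three months and after one and three years". Walking distance is the primary outcome and is measured at all four visits. For the analysis, "Repeated measurements within individuals will be managed through multilevel, random-effects models". The same section also says that "inferential statistics compare group differences", but the protocol defines no comparator group.

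**The concern.** An SD of 90 m between healthy people describes how far their walking distances spread around their mean. A before-after comparison depends on something else: how much each patient's own distance changes, and how variable that change is. The two are linked by SD of change = patient SD × √(2(1 − r)), so the conversion needs both the SD in these patients and r. The protocol gives neither.

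The stated 45 also lies close to the per-group size of a two-group comparison with 90 m and 53 m. That suggests a formula for independent groups was applied to a single cohort. If so, the only quantitative argument for the study size would rest on an input that does not match the design. A reader could not tell what power or precision to expect for the primary outcome. At 3–5 patients per centre per year in five centres (15–25 a year), 45 patients take about two to three years to recruit, so the question is a fair one.

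**Working it through.** **Inputs.** From the protocol: SD 90 m, difference 53 m, total 45. Assumed, because the protocol does not give them: two-sided 5%; 80% or 90% power; r between 0 and 0.8; patient SD 90 m unless stated otherwise.

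**Step 1: can 45 be reproduced?** At least three routes arrive at or next to it.

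- Two independent groups, 80% power: n per group = 2 × 90² × (1.960 + 0.842)² / 53² = 45.27 (46.25 with the t distribution). Rounded up this is 46 or 47, so 45 is only a near match. A paired calculation with r = 0 uses an SD of change of 90 × √2 = 127.3 m and gives the same 45.27 by the normal formula.
- Paired t-test, r = 0.3, 90% power: SD of change = 90 × √1.4 = 106.5 m, n = 44.4, rounded up to 45.
- SD of change taken as 90 m, 90% power, 30% loss: (90 × (1.960 + 1.282) / 53)² = 30.3, rounded up to 31; 31 / 0.7 = 44.3, rounded up to 45.

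The second and third routes are within-patient calculations. The printed number therefore does not show that a between-person SD was misapplied.

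**Step 2: what do 45 complete pairs give on the protocol's own figures?** Paired t-test, 53 m, noncentral t; half-width = t(44) × SD of change / √45.

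| r (assumed) | SD of change | Power | 95% CI half-width | n for 80% / 90% |
|---|---|---|---|---|
| 0 | 127.3 m | 78% | 38 m | 48 / 63 |
| 0.25 | 110.2 m | 88% | 33 m | 36 / 48 |
| 0.5 | 90.0 m | 97% | 27 m | 25 / 33 |
| 0.8 | 56.9 m | >99% | 17 m | 12 / 15 |

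**Step 3: where is the limit?** With 45 pairs, power reaches 80% as long as the SD of change is at most 124.1 m. At a patient SD of 90 m this means r ≥ 1 − 124.1² / (2 × 90²) = 0.05. For 90% power the limit is 107.3 m, or r ≥ 0.29.

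**Step 4: stress the inputs.** Each line gives power for r = 0, 0.25, 0.5 and 0.8.

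- Patient SD 70 m: 94%, 98%, >99%, >99%.
- Patient SD 110 m: 61%, 73%, 89%, >99%.
- Patient SD 90 m, and the 51 m change that the introduction cites from earlier plication work: 75%, 86%, 96%, >99%.
- Patient SD 90 m, 53 m, with 36 complete cases (an assumed 20% loss): 68%, 80%, 93%, >99%. This is an approximation, because the planned random-effects models can also use patients with partial follow-up.

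**The case for a change.** The strongest case for a change runs as follows. The protocol chose to print a required number and its inputs, so the inputs can be judged. A between-person SD from healthy people is the wrong kind of quantity for this design, and patients with diaphragmatic paralysis may vary more. At a patient SD of 110 m, 80% power needs r of about 0.36, and at r = 0 power falls to 61%. The introduction cites earlier plication work in which "6-minutes walking distance improved by 51 meters (6", and that source might hold a more relevant SD. Rewording costs little.

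Part of this stands. The SD of change or r is the missing piece, and one sentence giving it with alpha, power and test would make 45 traceable. The claim of a shortfall does not stand. The 61% requires two things together: a patient SD of 110 m, which appears nowhere in the protocol, and no correlation at all between the same patient's walks before and after surgery. At 110 m with r = 0.5, power is already 89%. The SD could also be lower than 90 m, and at 70 m no value of r from 0 to 0.8 gives less than 94%. Whether the cited plication work reports an SD of change cannot be told from the protocol.

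The sentence about group differences does not alter this. With a true two-group comparison, 45 in total would be about half of the 92 needed (2 × 46), but there is no second treatment group to compare.

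**Conclusion.** The concern identifies an incompletely reported sample-size basis, not an arithmetic error and not a study shown to be too small. The protocol states no power that the design then misses. On its own 90 m and 53 m, 45 complete pairs reach 80% power once r is about 0.05, and the only value below 80% in the main table is 78%, at r = 0. This rests on a two-sided 5% test, a paired reading inferred from the aim, visits and planned models, and a patient SD near 90 m. The patient SD and r remain unknown.

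A revision would gain little. It would keep 45, the visits and the within-patient models, and would replace one sentence with a range of power that depends on assumed inputs. The sample-size inputs do not enter the analysis: the confidence interval for the change in walking distance will come from the observed data, whatever SD was assumed in advance. Alpha and the test are details an analyst would settle in the ordinary way, and a statistical analysis plan that is not shown may already state them. No change to the plan follows.

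### Does the risk statement understate the study's burden by leaving out the CT scans and blood gas samples in the schedule?

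*Protocol*

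**What the plan says.** Under Ethical considerations, the protocol notes that the patients have already been accepted for the operation on clinical grounds. It then says: "They are not exposed to any additional risks in this study beyond being examined more thoroughly with surveys and questionnaires". The same sentence continues with "lung function and performance tests, and chest X-rays before and after the surgical procedure". CT and blood gases do not appear in it.

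Both appear elsewhere as study assessments:

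- **CT.** The section on computerised tomography of the thorax reads: "A CT with a standard protocol to identify and quantify lower lobe atelectasis". The Table of study assessments marks it at baseline and at 1-3 months.
- **Blood gas.** The Blood gas analysis section begins: "A capillary or arterial blood gas analysis obtains the partial pressure of". The table row, "Arterial/capillary" blood gas, is marked at baseline, 1-3 months, 12 months and 3 years.
- **Chest X-ray.** "Chest X-rays are acquired in full inspiration and expiration in frontal and lateral views", at all four visits. The risk sentence does name this one.

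On timing, Study design and population states: "Patients will be assessed preoperatively and postoperatively after one to three months and after one and three years". The table heads its 3-year column with a question mark.

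**The concern.** The risk sentence is worded as a closed list: nothing beyond these items. The schedule in the same document holds two further items, and they are not the mildest. CT brings ionising radiation beyond plain films, and an arterial sample is more invasive than a questionnaire or a walking test. A reader could conclude that the protocol declares the light procedures and passes over the heavier ones, which would give ethics review and patient information an incomplete basis.

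There is also a possible consequence for the data. If CT were routine at some of the five hospitals and not at others, postoperative scans might be missing by centre, and the atelectasis result could be distorted.

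**Working it through.** No sample size, power or error rate is involved, and the plan gives no figure to reproduce. The check is to count the schedule and set it against the risk sentence.

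**1. Is each scheduled procedure named in the risk sentence?**

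| Assessment | Scheduled times per patient | Named in the risk sentence |
|---|---|---|
| Questionnaires | 4 | yes |
| Lung function tests | 4 | yes |
| Performance tests (6-minute walk, sit-to-stand) | 4 | yes |
| Chest X-ray | 4 | yes |
| CT | 2 | no |
| Arterial or capillary blood gas | 4 | no |

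**2. Could the named terms cover the missing ones?** Not comfortably. The study aim lists "physical performance, subjective breathlessness, lung function, blood gases, and radiology", with blood gases apart from lung function, and CT and chest X-ray have separate headings and separate table rows. The omission is real.

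**3. How large could the added burden be?** The Statistics section gives 45 patients.

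- CT, if none is routine: 2 × 45 = 90. If the preoperative scan is routine: 1 × 45 = 45. If both are routine: 0.
- Blood gas, if none is routine: 4 × 45 = 180. If the queried 3-year visit is not held: 3 × 45 = 135. If all are routine: 0.

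The figures 90 and 180 are therefore ceilings. The protocol has no statement that places the true number within either range. The reference to a standard protocol for CT describes how the scan is acquired; it does not say that the scan is usual care.

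**4. Which parts of the worry fall away?**

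- Arterial puncture is not required, because a capillary sample is allowed.
- Chest X-rays come to at most 2 phases × 2 views × 4 visits = 16 exposures per patient. They are declared, so this count is no part of the mismatch.
- Missing CT by centre has no support in the text. The schedule asks for CT at two visits for every patient. Restricting the atelectasis outcome to scans obtained clinically would itself introduce selection by centre and indication.

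**5. What would a correction change?** The schedule, the outcomes, the 6-minute walking distance as primary outcome and the planned regression and multilevel models would all stay as they are. Only the ethics paragraph would read differently.

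**The case for a change.** The strongest case for a change is that the sentence is exclusive and, on the face of the document, incomplete. A risk statement belongs in the protocol and cannot be left to an analysis plan. The authors list chest X-rays as an addition although such films are common around thoracic surgery, so a reader cannot assume that CT was left out because it is routine. The stated purpose of the CT is to measure a study outcome. The repair would cost a few words.

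Much of this stands. The list and the schedule do not agree, and the protocol does not say which tests are extra to care. What does not stand is the step from an incomplete sentence to greater exposure than declared. The omission fits an oversight, and it fits equally well a view that CT and blood gases belong to the work-up and follow-up of these patients. Nor are the tests hidden: the methods and the schedule both set them out. Any harm to consent would have to show in the patient information or the ethics application. Neither is available here, and the Relevance of research section reports that approval has been granted.

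**Conclusion.** The observation is correct, but it is a slip of wording with no consequence for the study as planned. The risk sentence omits two scheduled procedures, CT at two visits and blood gas at four, the last of these under a column headed with a question mark. The added burden this could represent runs from nothing to 90 CTs and 180 samplings across 45 patients, and the protocol does not fix where in that range it lies. The claim that exposure exceeds what is declared is therefore unproven, and the worry about bias by centre is conjecture.

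Bringing the sentence into line with the schedule would be good housekeeping. It would change no assessment, analysis, result or conclusion, so no change to the plan is called for. This rests on two assumptions: that sites follow the schedule as written, and that the patient information, which was not available, describes the procedures patients undergo. If the patient information were found to omit CT or blood sampling, that would be a matter for that document and would need to be judged there.
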